Aim 2. To determine whether bupropion (vs escitalopram) will improve motivational deficits. *Hypothesis 2a:* Bupropion vs escitalopram will improve objective and clinical assessments of motivation in depressed patients with high CRP and anhedonia at baseline. *Secondary Endpoints:* EEfRT, SHAPS-C and MAP. *Predictors and Covariates:* Same as above. *Analysis plan:* MMRM with random intercepts will be used to examine effects of group, time and group x time interaction controlling for variations in baseline scores. Relevant covariates as indicated in Aim 1 will be included in these analyses as described above.

Hypothesis 2b: Improvement in VS-vmPFC FC will correlate with improved objective and clinical assessments of motivation. Analysis plan: Multivariate regression models will be used to examine linear associations between primary (VS-vmPFC FC) and secondary endpoints (EEfRT, SHAPS-C and MAP). Models will be adjusted for relevant covariates as indicated above. Separate analyses will be run for each behavioral outcome of motivation. Type I errors as a result of multiple testing will be controlled by Family-Wise Error correction.⁷⁷

Aim 3. To determine whether bupropion (vs escitalopram) will improve depression severity. Hypothesis 3 (Exploratory): Bupropion vs escitalopram will improve depressive symptoms in MD patients with baseline high CRP and anhedonia. Analysis plan: MMRM will be used to examine effects of group, time and their interaction on depression severity using the HAM-D-17. Relevant covariates as in Aim1 will be included.

Interim Analysis: After 16 subjects have completed the study, the blind will be broken by [name], and an effect size estimation will be made of between group differences in VS-vmPFC FC.* If the effect size is less than Cohen's d =0.3 at both fMRI time points (weeks 4 and 8), the study will be terminated. If the effect size is between a Cohen's d of 0.3 and 0.6 at either 4 or 8 weeks, the study will be continued

PI: [name] Sponsor: NIMH

focusing on the fMRI time point with the largest effect size. If the between group difference in VS-vmPFC FC is >0.6 (Cohen's d), the possibility of using the data as proof-of-concept for a larger trial will be discussed with the study sponsor (NIMH).

* Due to slow recruitment secondary to COVID 19, we have decided to conduct the interim analysis at 16 subjects as opposed to 20.

11. Power Analysis

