Hypothesis 1: Our preliminary data from depressed (major depression – MD) patients with high inflammation (CRP >2 mg/L, n=7) administered a dopaminergic agent, L-DOPA, and placebo control was used to estimate the anticipated change in VS-vmPFC FC in response to treatment (bupropion) and control (escitalopram) conditions in the proposed study. The expected change in FC in response to bupropion and escitalopram (the withinsubject effects of these conditions) was then used to calculate the effect size (ES) and sample size per group that will be required to detect a significant difference between the response to bupropion versus escitalopram (the between-subjects effect) with alpha= 0.05 and power >0.80. Accordingly, based on the mean and standard deviation for the change in FC after L-DOPA (0.2±0.16), we can expect a large ES for the expected within-subject effects of bupropion (Cohen's $d_7 = 1.25$, which would require only 8 subjects to detect). Based

Figure 1: Estimated power for between-subject comparisons of the FC response to bupropion versus escitalopram. Sample size (x-axis) and power (y-axis) for ES (d) = 0.97. The proposed total sample size of 40 (dashed line, n=20 per group) will yeild power >0.8.

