on the mean and standard deviation for the change in FC after placebo (0.07±0.10), we expected a medium effect size for the effects of escitalopram (Cohen's d₂ = 0.7), representing ~30-40% increase in FC and consistent with a ~30% placebo effect commonly observed in trials in MD patients.⁷⁸ Based on these expected within-subject effects for our treatment and control groups and the corresponding mean and standard deviations from our preliminary data, we estimate the between-group effect of the response to bupropion and response to escitalopram to have an ES Cohen's d = 0.97, which would require a total sample size of 36 (18 per group) for power >0.8 at alpha=0.05. Using 5000-fold resampling, with alpha = 0.05, sample power= 0.8, sample sizes of 18 per group (total sample size= 36) was large enough to estimate group differences. Figure 1 presents a graphical representation of the total sample sizes required for between-subject group comparisons of the FC response to bupropion versus escitalopram across the full range of power, demonstrating >80% power at the proposed total sample size of n=40. Hypothesis 2: For hypothesis 2a, the expect difference in motivation after bupropion versus escitalopram is based on the improvement in the EEfRT that has been previously established to be clinically and pharmacologically meaningful (≥10% change, 79, 80 representing a 0.10 increase in probability of hard choice choices) and standard deviations from our preliminary data for the EEfRT in MD patients. Thus, we expect a 0.10 ± 0.10 difference in mean probability of hard choices after bupropion compared to placebo and a medium to large ES (Cohen's d = 1.0), which will require a total sample size of 34 subjects (17 per group) for power >0.8 at alpha=0.05. For hypothesis 2b, our preliminary data on the relationship between VS-vmPFC FC and motivation, as measured by the EEfRT, demonstrated a correlation coefficient (r) of 0.43 (r² = 0.185). We expect a similar effect size for the relationship between change of FC and change in motivation and will need a sample size of 37 subjects to detect an overall relationship between change in FC and motivation with power >0.8 at alpha=0.05. Therefore, based on our sample size of n=40 (20 per group) we will have at least 80% power to detect significant differences for the proposed hypotheses to be tested under both Aims 1 and 2 at alpha=0.05.

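### The 80% power stated for Hypothesis 2b assumes one EEfRT test at 0.05, whereas Section 10 tests three outcomes under family-wise correction; at 0.05/3, EEfRT power with 40 patients is about 0.66 to 0.69

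*Combined protocol and SAP*

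**What the plan says.** Section 11 (Power Analysis, Hypothesis 2) takes r = 0.43 (r² = 0.185) from preliminary data relating VS-vmPFC connectivity to motivation measured by the EEfRT. It expects a similar correlation between the changes and says the study "will need a sample size of 37 subjects to detect an overall relationship between change in FC and motivation with power >0.8 at alpha=0.05". With 40 patients, 20 per group, it concludes that there is "at least 80% power to detect significant differences for the proposed hypotheses to be tested under both Aims 1 and 2 at alpha=0.05". No correlation is given for SHAPS-C or MAP, and multiplicity is not mentioned.

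Section 10 (Hypothesis 2b) relates connectivity to EEfRT, SHAPS-C and MAP. It says "Separate analyses will be run for each behavioral outcome of motivation" and "Type I errors as a result of multiple testing will be controlled by Family-Wise Error correction". The text names no procedure. The supporting citation (reference 77) is a paper on multiple-testing procedures whose title does not single one out. No rule says whether 2b succeeds on any one outcome, on EEfRT, or on all three.

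On model terms, the 2b paragraph says only "Models will be adjusted for relevant covariates as indicated above". Treatment group is listed under Aim 1 as a predictor, not a covariate. Hypothesis 2a carries over both predictors and covariates by reference; the 2b paragraph mentions covariates alone.

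**The concern.** The power statement uses an alpha that the plan will not apply to 2b, and covers one of the three outcomes. If the EEfRT correlation really is 0.43 and EEfRT has to pass at 0.05/3, the test misses it in about one trial in three, not the one in five that 80% power implies. This pilot is meant to inform larger mechanistic trials, so a non-significant 2b result would be read as stronger evidence against the link than it is.

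A second, separate point concerns interpretation. The plan expects the drug to shift both connectivity and EEfRT. A correlation pooled over arms can then arise because both measures differ by drug, with no link between the two changes among patients on the same drug. The 2b text does not settle whether arm is in the model, or whether 0.43 is meant within arm or pooled.

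**Working it through.** **Inputs.** From Section 11: r = 0.43, r² = 0.185, alpha = 0.05, 37 patients required, 40 analysed. From Section 10: three outcomes, family-wise correction. Assumed: two-sided tests, as sidedness is not stated.

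**1. Reproduce 37.** F test of one regression slope with fixed predictor: f² = r²/(1 − r²) = 0.185/0.815 = 0.227, noncentrality n·f², degrees of freedom 1 and n − 2.
- n = 36: power 0.793.
- n = 37: noncentrality 8.40, power 0.804.

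So 37 is the smallest n that reaches 80% for one unadjusted test. Fisher z gives 0.765 at n = 37 and needs 41, so the stated figure depends on the fixed-predictor method.

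**2. EEfRT power at n = 40.** The strictest step for three tests is 0.05/3 = 0.0167. For Fisher z, power = Φ(atanh(0.43)·√(n − 3) − z), with atanh(0.43) = 0.460 and √37 = 6.083, product 2.797.
- At 0.05: Φ(2.797 − 1.960) = 0.799.
- At 0.05/3: Φ(2.797 − 2.394) = 0.657.

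| Method, n = 40 | 0.05 | 0.05/3 |
|---|---|---|
| Fixed-predictor F (noncentrality 9.08) | 0.835 | 0.693 |
| Fisher z | 0.799 | 0.657 |
| Bivariate-normal simulation | 0.81 | 0.66–0.67 |

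Reaching 80% at 0.05/3 would take 50 analysed patients (F) or 53 (Fisher z). The 50 in the plan are randomised, to leave 40 with complete data.

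**3. If Hochberg is assumed.** Simulated EEfRT power at n = 40. The r for SHAPS-C and MAP and the correlation among outcomes (varied between 0 and 0.7) are assumptions.

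| r for the other two | Bivariate normal | Fixed predictor |
|---|---|---|
| 0 | 0.66–0.67 | 0.70 |
| 0.3 | 0.69–0.72 | 0.73–0.74 |
| 0.43 | 0.76–0.77 | 0.79–0.80 |

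If success on any one outcome sufficed, which the plan does not state, power would be about 0.68 to 0.83 with the other two r between 0 and 0.3, and about 0.85 to 0.96 with all three at 0.43.

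**4. Arm term.** For within-arm correlation w and standardised drug effects d1 and d2, with equal arms, pooled r = (w + 0.25·d1·d2)/√[(1 + 0.25·d1²)(1 + 0.25·d2²)]. With w = 0 and the plan's 0.97 and 1.0: 0.2425/√(1.2352 × 1.25) = 0.195. Simulation with 20 per arm and w = 0, share significant at 0.05:

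| d for connectivity, EEfRT | No arm term | Arm term |
|---|---|---|
| 0.97, 1.0 | 23% | 5% |
| 0.97, 0.5 | 10% | 5% |
| 0.5, 0.5 | 6.5% | 5% |

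These d values are illustrations. The first comes from L-DOPA data, where "placebo control was used to estimate the anticipated change in VS-vmPFC FC". The second is stated as a "difference in mean probability of hard choices after bupropion compared to placebo". Neither is a bupropion versus escitalopram estimate.

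With w = 0.43 and an arm term, Fisher z gives Φ(0.460 × 6 − 1.960) = 0.788 and Φ(0.460 × 6 − 2.394) = 0.643. Simulation gives 0.80 and 0.65, and the F test 0.825–0.835 and 0.679–0.692, depending on the noncentrality convention. The range is 0.79 to 0.84 at 0.05 and 0.64 to 0.69 at 0.05/3.

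**The case against.** The strongest reply is that no procedure is named, so 0.05/3 is the harshest case. A step-up method recovers some power, and an any-outcome rule with all three correlations at 0.43 would exceed 0.80. That stands as far as it goes: the shortfall is a range. But the favourable readings need correlations for SHAPS-C and MAP that the plan does not give, or a success rule that it does not state.

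A second reply is that 2b is a secondary hypothesis in a pilot, and that no stopping or success rule uses it; the interim analysis looks at connectivity only. This limits the consequence and is why no larger trial is requested. It does not make the power sentence correct.

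On the arm term, Section 11 speaks of an overall relationship, and Section 4 frames 2b as a correlation of changes with no within-drug claim. If the pooled association is the target, the 23% is power to detect a real pooled r of about 0.20, not a false-positive rate. Group may also carry over from Aim 1. The arm term is therefore a clarification, not a demonstrated error.

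Four stronger readings are tempting and not supported:
- That 37 is a miscalculation. It reproduces exactly for what it describes.
- That the correction also undermines the stated power for Hypotheses 1 and 2a. The correction sentence sits in the 2b paragraph only.
- That 0.43 is pooled and the true within-arm power is therefore far lower. That needs the borrowed d values and a reading the text does not fix. If instead 0.43 is within arm and no arm term is fitted, power under the same d values is about 0.97 at 0.05 and 0.92 at 0.05/3, partly from the drug effect.
- That the full covariate list will erode power further by a known amount. Section 10 screens covariates for association and selects by BIC, so no fixed set is planned.

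**Conclusion.** The mismatch is in the text and holds for 2b. The 80% statement is right for EEfRT alone at an unadjusted 0.05 (0.80 to 0.84 with 40 patients, depending on method). It does not describe the corrected test that Section 10 plans. If 0.43 is the correlation in the model tested, EEfRT power is about 0.66 to 0.69 at 0.05/3. Under an assumed Hochberg procedure it is about 0.66 to 0.77 by bivariate simulation, reaching about 0.80 only with the fixed-predictor formula and all three correlations at 0.43. Power for SHAPS-C and MAP cannot be assessed from the documents. This should be corrected, but it does not threaten the primary analysis.

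The arm-term point is secondary and rests on an ambiguity. The size of the problem it guards against depends on how far each drug shifts both measures.

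**What to change.** **For the mismatch.** In Section 10, name the family-wise procedure for the three 2b tests. In Section 11, do one of two things:
- restate 2b power with 40 patients at the alpha the procedure implies, naming the calculation method (about 0.66 to 0.69 for EEfRT at 0.05/3); or
- label the 80% figure explicitly as EEfRT only and before multiplicity correction.

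Calling it an EEfRT figure without the second half of that label would still quote an alpha that Section 10 does not use. Keep 37 as the size for one unadjusted regression, and leave the sample size as it is.

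**Separately, as an improvement.** In Section 10, state that treatment arm is a fixed term in each 2b model and that the within-arm (partial) association will be reported. In Section 11, say whether 0.43 is assumed within arm or pooled. For a within-arm 0.43 with an arm term and no other covariates, power with 40 patients is about 0.79 to 0.84 at 0.05 and 0.64 to 0.69 at 0.05/3.

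**Cost.** A few sentences in two sections, one degree of freedom for arm, and a less favourable stated power for a secondary hypothesis in a pilot.

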Criteria for Study Discontinuation ("Stopping Rules"):

Individual:

To reduce the risks associated with active treatment, all subjects will be monitored carefully for the development of adverse events as well as worsening of their condition. Between signing consent and completing the screening assessment, a period of no more than 2 weeks will pass until baseline. Subjects will be closely evaluated throughout the study both virtually and during study visits for worsening of psychiatric symptoms. Moreover, all patients are provided 24/7 access to study personnel in the event of an emergency. Subjects will be discontinued at any point for any of the following: 1) the development of significant suicidal ideation, plan or intent as determined by spontaneous subject report or as determined by CSSRS,⁴¹ 2) the development of psychotic or catatonic symptoms, 3) a 25% increase from baseline of HAM-D-17 score, 4) missing more than 2 consecutive doses of medication more than once during the study, and 5) positive pregnancy test. Subjects requiring discontinuation will be referred for further evaluation and treatment by one of the study psychiatrists.

1) If more than two individuals experience a reportable serious adverse event related to study procedures within a six-month period, the study will be stopped and reviewed by the DSMB.

Neuropsychiatric Assessments

Structured Clinical Interview for DSM-V Axis I Disorders (SCID-V) is a semi-structured clinical interview that provides a wide range of DSM-V diagnoses. ⁴² All patients will be evaluated by a modified SCID as part of the screening process. In addition to providing information for inclusion/exclusion purposes, the SCID will provide data about psychiatric predictors of treatment response, including number of past major depressive episodes, length of the current episode and presence of co-morbid anxiety disorders and/or dysthymia.

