Aim 1: To determine whether bupropion (vs escitalopram) will increase FC in reward circuitry. Hypothesis 1: Bupropion vs escitalopram will increase VS-vmPFC FC in depressed patients with high CRP and anhedonia at baseline. Primary Endpoint: Targeted VS-vmPFC FC at 8 weeks. Predictors: group (bupropion vs escitalopram), time (baseline, 8 weeks), and group x time interactions. Covariates: Primary: Age, sex, BMI, race. Additional covariates: Number of depressive episodes, length of current depressive episode (in months), treatment trials (ATRQ), age of onset, and family history of depression (ves/no), weeks on targeted dose of medication, Analysis Plan: Subjects will be randomized to two different treatment groups and scanned across two visits. Consequently, a factorial mixed-effects models for repeated measures (MMRM) will be employed with group, time and group x time interaction on targeted VS-vmPFC FC as fixed effects and each subject's baseline (identity) as random effects. Linear and multi-level mixed effects will be evaluated using both unstructured and autoregressive covariance structures and restricted maximum likelihood estimation and will be used to predict random effects (slope and intercept) in addition to fixed effects, optimized using Bayesian Information Criteria (BIC). Primary and additional covariates will be entered in all models as random variables after testing for significant associations. Given the inherently noisy nature of the covariates, model tuning to optimize the balance between explanatory (r²) and noise variables (root mean square error) will be undertaken to select the most parsimonious models using BIC. The MMRM will also be augmented using Elastic net generalized regression models using group||time nesting approaches. Models will be selected using model comparison metrics. All analyses will be conducted in accordance with published guidelines.⁷⁶ Exploratory analysis: A similar analysis as indicated above will be conducted on fMRI scans conducted at 4 weeks. The 4-week scan will be conducted based on the rapid effects seen with dopamine agonists in our preliminary studies with L-dopa (data not shown).

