To minimize discomfort during the fMRI scanning, patients will be provided with a head cushion and ear plugs. Patients will also be informed about the progress of the procedure through a remote microphone. In the case of patients developing acute anxiety or panic the scanning session will be terminated and patient provided enough support to cope with the feelings induced by the scanner. Bupropion or Escitalogram Treatment:

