urine toxicology, self-report surveys and medication check			
Computer Task (depending on choice	\$5-\$30	\$5-\$30	
made on the computer)			
Complete Scan	\$150		\$150
Incomplete Scan	\$25**	\$25**	
(Visit Total)	\$80-\$230		
Virtual (Week 6)	\$25	\$25	
(Visit Total)	\$25		
Visit 6 (Week 8)			
Medical and psychiatric assessments,	\$50	\$50	
research bloods, urine toxicology,			
self-report surveys and medication			
Check	\$5-\$30	\$5-\$30	
Computer Task (depending on choice made on the computer)	\$5-\$50	\$5-\$30	
Complete Scan	\$150		\$150
Incomplete Scan	\$25**	\$25**	
(Visit Total)	\$80-\$230		
Total Study Compensation	\$425-\$935		

^{*}Screening visit may be divided across 2 visits and paid \$25 per visit

Potential benefits of the proposed research to the subjects and others:

The direct benefits of study participation will include receiving a psychiatric and medical evaluation, including standard blood and urine-based laboratory tests and MRI scan. In addition, subjects will all receive an active treatment with known efficacy. Subjects will also have the chance to contribute to a scientific investigation, which may be of benefit to future patients. Benefits to others may include gaining significant knowledge regarding the role of inflammatory activation in the pathophysiology and treatment of depression. As a result of this knowledge, this study may contribute to personalization of therapeutic strategies for patients with major depression.

Given the low risk involved with blood drawing, psychiatric assessments and fMRI scanning coupled with the likelihood that many patients will obtain at least some symptomatic benefit, we feel that the risks of the study are reasonable in relationship to the benefits of study participation. Importance of the knowledge to be gained:

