Successful treatment modalities both arise from, and contribute to, our understanding of disease pathophysiology. Mounting data indicate that depression is associated with evidence of immune/inflammatory activation, and that patients with major depression may be especially likely to demonstrate increased proinflammatory cytokine production/release. Furthermore, alterations in dopamine neurotransmission have been demonstrated extensively in individuals exposed to inflammatory stimuli, and patients with major depression have been shown to exhibit inflammation-associated alterations in functional connectivity within dopamine-related reward circuitry. Nevertheless, studies conducted to date have not explored whether currently available antidepressant treatments have

^{**}Unable to complete scan leading to termination from the study

PI: [name] Sponsor: NIMH

differential effectiveness in reversing inflammation-related brain changes and whether any observed differential effects on the brain are manifested in behavior. Understanding the mechanisms by which conventional antidepressant treatments interact with immune-related pathologies may not only lead to new treatments for depression but also may help guide antidepressant choice by measuring inflammatory state prior to treatment. For these reasons, we feel that risks to subjects are reasonable in relationship to the value of the knowledge (both theoretical and practical) to be gained. Investigational Drug Status

All drugs to be used in this study (bupropion and escitalopram) are FDA-approved for the treatment of depression and will be used at doses and duration recommended in the package inserts of these medications.

14. Data and Safety Monitoring Plan (DSMP)

The DSMB for this study will consist of [name]. Chairman, [name]., [name], M.S. and [name]. Each of these clinical researchers has agreed to serve as the external DSMB for investigator-initiated clinical trials conducted by Emory researchers in the Department of Psychiatry & Behavioral Sciences. If the DSMB requires additional specialized expertise to evaluate safety issues related to the performance of this study, a relevant specialist will be consulted by the DSMB. The frequency of the Department of Psychiatry and Behavioral Sciences DSMB review for this protocol will be once every year based on IRB recommendations consistent with the assessed risk status of the study.

Procedures and Responsibilities of the Emory DSMB

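### The documents contradict themselves on whether an incomplete scan ends participation; read literally, the payment footnote would cost a randomised patient the week-8 primary scan and all later outcomes

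*Combined protocol and SAP*

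**What the plan says.** **Payment table (section 13, Compensation to Participants).** A line labelled "Incomplete Scan", paying $25 and marked with two asterisks, appears at Visit 3 (baseline), Visit 5 (week 4) and Visit 6 (week 8). The footnote to that mark reads "Unable to complete scan leading to termination from the study". The last row, "Total Study Compensation", gives $425 to $935.

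**Discontinuation lists.** Section 5 (Criteria for Study Discontinuation) opens its list with "Subjects will be discontinued at any point for any of the following". Section 13 gives similar lists under the treatment-risk text and again under Stopping Rules, the latter at the investigator's discretion. They cover suicidality, psychotic or catatonic symptoms (in places also manic symptoms), worsening HAM-D-17, missed doses and pregnancy. One list, for the period between screening and baseline, adds hospitalisation and imminent threat. None names an incomplete scan.

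**Scanner text.** Section 13 (fMRI scans) says: "In the case of patients developing acute anxiety or panic the scanning session will be terminated". The Faces Task description in section 5 takes a distressed patient out of the scanner. Neither says that the patient leaves the study.

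**Role of each scan.** Section 10, Aim 1, states "Primary Endpoint: Targeted VS-vmPFC FC at 8 weeks" and gives the time factor as "time (baseline, 8 weeks"). The week-4 scan comes under exploratory analysis: "A similar analysis as indicated above will be conducted on fMRI scans conducted at 4 weeks". The Interim Analysis paragraph also uses the week-4 effect size and allows the study to continue on whichever scan time point shows the larger effect.

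**The concern.** Site staff have no single rule. One part of the protocol links an incomplete scan to the end of participation, and the other relevant parts do not.

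The consequence depends on the visit. At baseline the scan comes before randomisation, so a failed scan is a pre-randomisation loss. Week 8 is the last visit, so little remains to be lost. Week 4 is different. Under the literal reading a randomised, treated patient would leave because of a scan that the primary model does not use, and would forfeit the scan that it does use. EEfRT, SHAPS-C, MAP and HAM-D-17 are collected outside the scanner, yet their remaining values would go too. That is a post-randomisation loss that the plan could avoid, and the documents describe no outcome collection after termination.

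**Working it through.** **1. Does the payment table apply the termination reading?** Inputs are the visit totals in the table.

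- Minimum: 50 + 55 + 80 + 55 + 80 + 25 + 80 = $425. This matches the stated minimum.
- Maximum: 50 + 60 + 280 + 60 + 230 + 25 + 230 = $935. This matches the stated maximum.
- Each $80 is 50 (assessments) + 5 (lowest computer-task payment) + 25 (incomplete scan).

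The $425 therefore describes a participant with incomplete scans at baseline, week 4 and week 8 who still attends every visit. If an incomplete scan ended participation, the lowest totals would be different:

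| Course under the termination reading | Lowest total |
|---|---|
| Ends at incomplete baseline scan | 50 + 55 + 80 = $185 |
| Ends at incomplete week-4 scan, baseline complete | 50 + 55 + 255 + 55 + 80 = $495 |
| Incomplete only at week 8 | 50 + 55 + 255 + 55 + 205 + 25 + 80 = $725 |

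Here 255 = 50 + 5 + 200 and 205 = 50 + 5 + 150, the lowest totals with a complete scan. None of these equals $425, so the table and its footnote do not agree.

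**2. What would a week-4 termination remove?** From Table 1 in section 5:

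| Measure | Scheduled after week 4 |
|---|---|
| fMRI (primary FC) | week 8 |
| EEfRT | week 8 |
| HAM-D-17 | week 8 |
| SHAPS-C | weeks 6 and 8 |
| MAP | weeks 6 and 8 |

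Section 4 also lists week 6 for EEfRT and HAM-D-17. Table 1 does not, and Table 1 is used here.

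**3. How large could the loss be?** The documents give no scan-failure rate, so any figure is an assumption.

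- Attrition allowance (section 5): 20% of 50 = 10 patients.
- Assumed week-4 failure of 2% to 10% of 50 = 1 to 5 patients, or 10% to 50% of that allowance.

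The plan's own sample size (section 11) comes first. The pooled SD is √((0.16² + 0.10²)/2) = 0.1334 and d = (0.20 − 0.07)/0.1334 = 0.974, which the plan gives as 0.97. A two-sided two-sample t test with noncentrality d√(n/2) on 2n − 2 degrees of freedom gives 78.3% power at 17 per arm and 80.7% at 18. The stated 36 in total is reproduced.

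If week-4 failures came on top of the 20% attrition:

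| Assumed extra loss from 40 | Patients analysed | Power at d = 0.97 |
|---|---|---|
| none | 40 | 84.8% |
| 5% | 38 | 82.9% |
| 10% | 36 | 80.7% |
| 15% | 34 | 78.3% |
| 20% | 32 | 75.6% |

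If the 20% already covers scan failures, planned power does not change.

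**The case against.** The strongest reply is that this is a payment footnote and not a rule of conduct. It contains no instruction. It can be read as saying when the $25 is due, namely for a scan failure of the kind that led to termination. The discontinuation lists, the scanner text and the $425 minimum all fit that reading better. This stands. A reader might infer that the protocol requires termination after any incomplete scan, but the documents do not support that. They support only that the passages disagree. The $425 is not decisive either way, since it may be no more than a mechanical sum of the visit minima.

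Four further limits also stand.

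- The documents do not define an incomplete scan. One might infer that a patient who finishes the resting-state run and stops in a later task would be terminated, but nothing says so. A completed resting run would also preserve only part of the imaging, because Aim 1 uses both resting-state and task-based connectivity.
- A patient who cannot finish at week 4 may also fail at week 8, so the lost primary scan is not wholly due to the footnote. The non-scanner outcomes would still be recoverable.
- The exploratory label is not the whole story, because week 4 enters the interim rule. That makes keeping the completed sequences more useful, not less.
- One might infer that the loss would differ by arm through anxiety or symptom change. That is possible, but the documents give no data on it.

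**Conclusion.** There is an internal contradiction, and it should be resolved. The payment footnote links an incomplete scan to the end of participation, while the discontinuation lists, the scanner text and the table's own minimum do not. The contradiction is clear from the text and the arithmetic. Whether termination is the operative rule cannot be settled from the documents.

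Under the literal reading, each randomised patient affected at week 4 loses the week-8 primary scan and the later clinical and behavioural outcomes. How many patients that means is unknown. The range of 1 to 5 patients rests on an assumed failure rate. The power figures rest on a further assumption, that these losses add to the 20% attrition. A claim that the trial is underpowered for this reason would go beyond the documents: power stays above 80% even with an assumed extra 10% loss, and is unchanged if the allowance already covers failed scans. The case rests on avoidable post-randomisation loss in a trial that plans to analyse 40 patients.

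**What to change.** Reconcile the footnote with the discontinuation lists in sections 5 and 13, the scanner text in both sections and the $425 total. State plainly whether an incomplete scan ends participation, and at which visits.

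For data collection after randomisation:

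- treat an incomplete scan as missing data for the sequences not acquired;
- keep the sequences that were completed;
- continue to collect the remaining scheduled outcomes, including offering the week-8 scan.

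Decisions on stopping study treatment stay with the sponsor's reconciled discontinuation lists. This matters because section 13 ties early termination to possible unblinding and to medication steps, so this point proposes no rule on treatment.

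The cost is an edited footnote and a matching sentence in section 5, with no visits or procedures beyond those already scheduled. The small downside is that some patients will have clinical data without complete imaging.
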